1. PURPOSE OF THE STUDY AND BACKGROUND

1.1: Purpose of the Study:

Inactivated influenza vaccine (“IIV”) is an intramuscular vaccine administered to children ≥ 6 months in age that is composed of highly purified HA and NA surface glycoproteins and contains trace, if any, activators of the immune system. In contrast, live attenuated vaccine (“LAIV”) consists of intranasally delivered, attenuated viruses that stimulate the innate immune system while undergoing limited viral replication in the upper respiratory tract. Some children also continue to first encounter influenza through natural infection, where high levels of viral replication stimulate vigorous innate immunity. Although CD4 T cells play a key role in regulating the influenza-specific B cell, CD8 T cell, and innate immune responses, little is known about the immediate and long-term effects these different routes of early childhood priming have on CD4 T cell mediated immunity. The long-term goal of this research is to understand how a child’s early exposure to influenza shapes immunity and poises the immune system to respond to subsequent influenza challenge. Our objective is to determine how the anti-influenza CD4 T cell and antibody responses are altered by the mode of primary influenza encounter and establish the consequences this has on subsequent influenza vaccination. To accomplish this objective, we will enroll two cohorts of young children: 1) a cohort of 24 through 35 month of children administered either LAIV or IIV and 2) a separate cohort of infants first exposed to influenza through prime-boost administration of IIV or natural infection during their initial influenza season. All enrolled subjects will be followed longitudinally to the subsequent influenza season and then rechallenged with IIV. These cohorts of children will allow us to test the following hypotheses:

- 1) Compared to intramuscular IIV, initial exposure to intranasal LAIV establishes a greater and more polyfunctional CD4 T cell response in children 24 through 35 months of age
- 2) Compared to a first exposure to influenza through infection, primary infant vaccination with IIV establishes a more limited CD4 T cell repertoire that consists predominately of IL-2 producing cells, and
- 3) The CD4 T cell responses established with this initial priming will differentially poise subjects to respond to revaccination with IIV the following influenza season

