Figure 2: Expansion of CD4 T cells directed against conserved peptides is seen following pandemic H1N1 vaccination, with a correlation between the development of an HA-specific CD4 T cell response and neutralizing antibody titer. Subjects received the monovalent inactivated subvirion A/California/07/09 vaccine and CD4 T cell responses against conserved and nonconserved peptide pools were examined by IFN γ Elispot assay using CD8 and CD56 depleted PBMCs. While a response to HA (A) and NP/M1 (B) peptide pools expected to be conserved compared to recently circulating H1N1 strains was detected, little response to peptides expected to be unique to this virus was seen in subjects without prior immunity (C). Error bars represent the standard error of the mean and P-values calculated using Wilcoxon signed rank test. Development of a CD4 T cell response was correlated with the maximum microneutralization titer achieved (D). R- and p-values determined using the Spearman correlation coefficient.

- To evaluate in an unbiased way the influence of previous influenza exposure on PBMC gene expression patterns using RNA-seq analysis
- To assess the mucosal immunity established by these modes of priming and determine whether any initially established differences in mucosal immunity are maintained on subsequent rechallenge with IIV

To accomplish these objectives, we plan to enroll a cohort of 60 children who have previously been vaccinated with at least 2 doses of IIV and who are between the ages of 24 and 35 months into cohort 1. These children will be block randomized to receive either LAIV (n=30) or IIV (n=30) in groups of 5 unless a history of isolated wheezing in the past year is present. As LAIV is not indicated in children with a history of recent wheezing, otherwise eligible children who have a history of wheezing will be defaulted to receive IIV. Children will have a blood draw and nasal wash on study entry and again at days 10 (+ 4 days/- 2 days) and 24 (+/- 4 days) post vaccination. They will then be followed through to the subsequent influenza season, when they will be rechallenged with IIV with blood draws and nasal washes pre-vaccination and again at days 10 (+ 4 days/- 2 days) and 24 (+/- 4 days) post vaccination (Figure 3).

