- The procedure to conduct blood draws and nasal wash specimens in the home setting will be the same as that used in outpatient setting (see home visit SOP). An experienced pediatric research nurse will go on all study visits to complete the blood draw. This nurse will be accompanied by either the study PI or a research assistant trained in how to hold subjects to optimize the success of blood collection. If blood is unable to be obtained, this will be documented on the Case Report Form. There will not be a requirement for the subject to present to the VRU in the event blood is unable to be collected.
- To ensure the safety of the researchers, study personnel will travel to the patient's residence in pairs. All compensation payments will be made either by Bank of America VISA Prepaid card or by check mailed to the subject after the study visit. When a Bank of America VISA card is used, the card will carry no balance on being handed to the patient. The \$25 will be added to the card by study personnel on return to the hospital following completion of the study visit. Members of the research team will be mandated reporters. In the event that potential child abuse or neglect is observed, the case will be reported to Child Protective Services as required. The consent form will

include mandatory reporting language to inform parents that the members of the research team are required to report any observed or suspected child abuse or neglect.

6. CONCOMITANT AND DISALLOWED MEDICATIONS:

There are no restrictions on the medications that can be provided during the course of the study. All medications necessary for the health and well-being of the child will be allowed. All medications used during the study will be recorded on the data collection form and updated at each study visit. No medications other than yearly seasonal influenza vaccine will be administered as part of this study.

7. SUBJECT WITHDRAWALS:

Subjects may withdraw consent for study participation at any time during the study without penalty. The subject will also be considered a study withdrawal if they are lost to follow up or are unable to comply with study procedures or visits.

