13. DATA ANALYSIS AND MONITORING

13.1: Sample Size Determination:

	d=0.3	d=0.35	d=0.4
n1=25, n2=25	0.738	0.858	0.934
n1=30, n2=30	0.815	0.915	0.968
n1=35, n2=35	0.871	0.95	0.985
n1=30, n2=10	0.517	0.646	0.761
n1=30, n2=15	0.64	0.772	0.871
n1=30, n2=20	0.721	0.844	0.924

The primary endpoint of this study is CD4 T cell responses. Based on a study of immune response in children and adults (62), the overall mean percentage of IFN γ + CD4 T cells in 5-9 year old children vaccinated with IIV or LAIV is around 0.1%, or -3 in log₁₀ scale. The standard deviation (STD) in log₁₀ scale is around 0.4. The geometric mean differences induced by vaccinations or between the two types of vaccination is around 0.3 in log₁₀ scale. The above table summarizes statistical power based on Student's two sample *t*-test. Assuming our responses are similar, recruiting n=30 subjects in each group will give us adequate power (0.815) for Aim 1. Because LAIV is an attenuated virus, it is reasonable to assume that the difference in CD4 T cell responses induced by IIV and natural influenza infection is larger (d=0.4), therefore recruiting

n=30 subjects in the IIV group and n=15 subjects in the infection group can achieve adequate power (0.871) for Aim 2. For Aim 3, assuming that within-group STD is 0.4 and between-group STD is just 0.2, the power is 0.851 if we recruit n=105 subjects divided them into four subgroups (n1=30, n2=30, n3=30, n4=15).

13.2: Planned Statistical Analysis:

We outline the statistical analysis strategies for the specific aims as follows. **Aim 1:** A cohort of n=60 healthy children will be recruited and divided into two groups with equal sample size (n=30); one group will be vaccinated with LAIV and the other with IIV. Their T cell and antibody responses will be measured at three time points: Baseline, day 10, and day 24 post-vaccination. We will apply Shapiro-Wilk's test to check the normality. If the data passes the normality test, two sample *t*-tests will be used to detect significant mean difference between the two groups at each time point. Otherwise, Wilcoxon rank-sum test will be used. Because multiple response variables are used in this analysis, the *p*-values will be adjusted by the Benjamini-Hochberg multiple testing procedure (80) to control the false discovery rate (FDR) at the level of 0.05. In addition to pairwise comparisons, the following linear mixed effect model will be used to analyze data collected from all time points:

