$$y_{kit} = \alpha_k + \beta_k G(i) + \gamma_{kt} + \delta_{kit}. \quad (0.1)$$

Here y_{kit} represents the k th response variable measured from the i th subject at the t th time point; α_k is the overall mean value of y_{kit} ; $G(i)$ is a binary variable which equals 0 if the i th subject is vaccinated with LAIV and 1 otherwise; β_k is a linear coefficient that quantifies the magnitude of the group-effect; γ_{kt} is a random effect term that quantifies the time effects; and δ_{kit} represents independent measurement errors. Likelihood ratio test will be used to test $H_0: \beta_k = 0$ against $H_1: \beta_k \neq 0$. **Aim 2:** Two groups of infants will be recruited for this aim. The first group (n=30) will receive a prime-boost IIV series; the other group (n=15) consists of infants who are infected by influenza naturally. Multiple clinical endpoints will be recorded at 3 time points for both groups. We will apply two sample *t*-test (or Wilcoxon rank-sum test, if Shapiro-Wilks test rejects the assumption of normality) at each time point to detect significant group differences. In addition, we will apply a linear mixed effect model similar to Equation (1.1) to detect the overall group effect. The resulting *p*-values will be properly adjusted to control for FDR at a 0.05 level. **Aim 3:** All subjects (four subgroups; n=105) will be followed longitudinally for a year and then be revaccinated with IIV. CD4 T cell responses, antibody responses, and transcriptional profile (high-throughput RNA-seq) will be measured at three time points: prior to IIV re-vaccination, d10 and 24 days post re-vaccination. We will apply one-way ANOVA *F*-test (or Kruskal-Wallis test, if the normality assumption is rejected) to detect significant group differences at each time point. Post-hoc analysis based on Tukey's adjustment will be used to test for significant differences between groups. We will also apply a linear mixed effect model similar to Equation (1.1) to detect the overall group effect. For high-throughput transcriptional data, first we will apply suitable pre-processing techniques such as non-specific filtering (81), normalization (82) and batch-effect removing

(83). We then select differentially expressed genes at each time point by specialized procedures such as DEseq (84) and DEGseq (85). Benjamini-Hochberg procedure will be used to control FDR at a 0.05 level for all analyses.

13.3: Data and Safety Monitoring:

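### Hypothesis 3 concerns the response to revaccination, but every stated Aim 3 test compares group levels and none tests whether the rise from visit 4 differs

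*Combined protocol and SAP*

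**What the plan says.** Section 1.1, hypothesis 3, states that the CD4 T cell responses set up by priming "will differentially poise subjects to respond to revaccination with IIV the following influenza season".

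Section 13.2 takes measurements before revaccination (visit 4) and at days 10 and 24 afterwards (visits 5 and 6). It names four analyses for Aim 3:

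- A one-way ANOVA F-test, "or Kruskal-Wallis test, if the normality assumption is rejected) to detect significant group differences at each time point".
- Post-hoc pairs, where Tukey's "adjustment will be used to test for significant differences between groups".
- A longitudinal model: "We will also apply a linear mixed effect model similar to Equation (1.1) to detect the overall group effect". The only equation printed, (0.1), has one group coefficient, one time term and an error. It has no group-by-time term and no visit-4 covariate.
- For RNA-seq: "We then select differentially expressed genes at each time point by specialized procedures".

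Section 13.1 gives the Aim 3 power for n = 30, 30, 30 and 15: "assuming that within-group STD is 0.4 and between-group STD is just 0.2, the power is 0.851".

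The one place that uses a within-child change is section 5.5. There, a rise between the last year-1 visit and visit 4 flags an undocumented infection.

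**The concern.** A day-10 level is the level carried over to visit 4 plus the rise after revaccination. Hypotheses 1 and 2 predict that the priming routes leave different CD4 responses. If these persist even in part, the groups already differ at visit 4, and they will differ at day 10 even when every group responds identically. Conversely, if the groups that start higher rise less, day-10 levels can coincide while the responses truly differ.

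The overall group effect does not help, because it averages visit 4 with the two post-vaccination visits. Reading the visit-4 and day-10 tests side by side does not help enough either. Significance at one visit and not at another is not a test that the rise differs. The planned tests could therefore be taken as support for hypothesis 3 when there is none, or miss support that exists.

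**Working it through.** **Inputs.** From section 13.1: SD 0.4 log10 and group sizes 30/30/30/15 (N = 105). Assumed: alpha 0.05 before any Benjamini-Hochberg adjustment; the same SD at each visit; correlation rho between visits of 0.3, 0.5 or 0.7 (the documents give none); and the size and location of any carried-over gap.

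**Formula.** The power of the F-test is that of a noncentral F with 3 and 101 df and noncentrality λ = Σ nⱼ(mⱼ − m̄)² / SD², where m̄ is the weighted mean.

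**The plan's figure.** Section 13.1 does not state a pattern of means. With the infection group 0.4 above three equal groups, the SD of the four means is 0.2. Then λ = (15 × 90/105) × 0.4² / 0.4² = 12.86 and power is 0.852, against the stated 0.851. This is power for levels at one visit. The same pattern carried over to day 10 unchanged, with no difference in response, would give the same 0.852.

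**Case 1: equal rises.** With a gap g in the LAIV-primed and infection groups (45 children against 60), λ = (45 × 60/105) × g²/0.16.

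| Gap g | λ | Day-10 F-test rejects |
|---|---|---|
| 0.10 | 1.61 | 0.157 |
| 0.15 | 3.62 | 0.315 |
| 0.20 | 6.43 | 0.532 |
| 0.30 | 14.46 | 0.894 |

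With the gap in the infection group alone, the rejection rates are 0.587 (g = 0.3) and 0.852 (g = 0.4). For a single Tukey pair (critical t = 3.694/√2 = 2.612, 101 df), gaps of 0.2 and 0.3 reject in 0.255 and 0.616 of trials for 30 against 30, and in 0.157 and 0.409 for 30 against 15. A test of the rise rejects in 0.05 throughout.

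**The rise.** Its SD is 0.4 × √(2(1 − rho)), so λ for the rise is the level λ divided by 2(1 − rho).

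**Case 2: can the visit-4 test sort this out?** Joint results come from 20,000 simulated trials per cell (bivariate normal, gap in the LAIV-primed and infection groups).

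| | rho 0.3 | rho 0.5 | rho 0.7 |
|---|---|---|---|
| SD of the rise | 0.473 | 0.400 | 0.310 |
| Gap 0.2, equal rises: day 10 significant, visit 4 not | 21% | 17% | 14% |
| Gap 0.3, equal rises: day 10 significant, visit 4 not | 8% | 7% | 6% |
| Gap 0.3, equal rises: both significant | 81% | 82% | 83% |
| Gap 0.3, higher groups rise 0.2 more: both significant | 90% | 89% | 90% |
| Same, rise test | 39% | 53% | 77% |

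The pattern of both visits significant is about as common with equal rises as with unequal ones. The rise test separates them: 5% against 39% to 77%.

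**Case 3: day-10 levels coincide because the higher groups rise less.** The day-10 test rejects in 5%. The rise test rejects in 0.758/0.894/0.989 (gap 0.3) or 0.393/0.532/0.775 (gap 0.2) at rho 0.3/0.5/0.7. Visit 4 on its own is significant in 89% or 53% of trials, so the pattern seen is most often a gap at visit 4 only.

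**The case against.** The strongest reply is that hypothesis 3 does not force the rise to be the estimand. Retained memory is part of being poised, and the post-revaccination level is a legitimate endpoint. Visit 4 is also tested, and a reader would see group means at all three visits. That is true, and it is why the level tests should stay. But means seen by eye are not a test, and the plan does not say which quantity answers hypothesis 3.

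Other points have partial force:

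- A model merely similar to the printed equation could include an interaction. Its stated target is still the overall group effect.
- An analysis of the post-vaccination level adjusted for visit 4 is an alternative, with power 0.886/0.941/0.992 at rho 0.3/0.5/0.7 for the 0.4 infection-group pattern if true visit-4 means are equal. When those means differ, as hypotheses 1 and 2 would suggest, adjustment and change answer different questions.
- The match to 0.851 rests on an inferred pattern. A 0.4 difference in a group of 30 has the same between-group SD but gives λ = 30 × 75/105 = 21.43 and power 0.979.
- The gaps are assumed, and at 0.1 the day-10 test rejects in only 16%.
- A rise test does not remove confounding. Cohort 2 is younger and not randomised, and in cohort 1 children with recent wheezing default to IIV.

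None of these supplies the missing test.

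**Conclusion.** The concern holds and should be fixed. One of the three stated hypotheses has no direct test. With equal rises and a carried-over gap of 0.2 to 0.3 log10 in two groups, the day-10 F-test rejects in 53% to 89% of trials. With a true difference in rise masked at day 10, that test has only its 5% null rate, while a rise test has power 0.39 to 0.99 over the range examined. These sizes depend on the assumed gaps and correlations, and on the plan's SD of 0.4 holding at each visit. The absence of a test on change depends on none of them.

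**What to change.** In section 13.2, name the estimand for hypothesis 3 and pre-specify one of these:

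- a four-group comparison of the log10 change from visit 4 to visit 5 and to visit 6, with Tukey pairs; or
- the group-by-visit contrast in a mixed model with fixed visit effects and a random effect for child.

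Keep the level tests at visits 4 to 6 as a separate analysis of persistence (visit 4) and of post-revaccination level (visits 5 and 6). The mucosal objective in section 2.1, which asks "whether any initially established differences in mucosal immunity are maintained on subsequent rechallenge with IIV", needs them. State that a difference at one visit and not at another will not be read as a different response. Restate the Aim 3 power for the chosen contrast.

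The cost is wording only; no visit or sample is added. There are two downsides to disclose.

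- **Noise.** Below a correlation of 0.5 the rise is noisier than the level. The 0.4 infection-group pattern has power 0.70/0.85/0.98 on the rise at rho 0.3/0.5/0.7. Tukey-pair power on the rise is 0.44/0.62/0.87 (difference 0.3, 30 against 30) and 0.53/0.71/0.93 (difference 0.4, 30 against 15).
- **Failed draws.** A simple change needs blood at both visits, and section 5.11 says of home visits: "There will not be a requirement for the subject to present to the VRU in the event blood is unable to be collected". Suppose that draws fail independently at rate p, so that n and λ shrink by (1 − p) for the level and (1 − p)² for the change. At an assumed 10%, power on the change is 0.60/0.76/0.94 against 0.81 for the level. At 20% it is 0.48/0.64/0.87 against 0.75. The mixed model lessens this loss because it keeps children with only one draw.

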The second cohort of children will be infants between 3 and 12 months of age who will be enrolled to investigate how the primary CD4 T cell response that develops following IIV administration differs from that established after natural influenza infection. Infants who receive vaccine in this cohort will be at least 6 months of age and will be enrolled in the fall before influenza begins to circulate in the community. Infants between 3 and 12 months of age who contract a natural influenza infection before any doses of vaccine are administered will be eligible for the natural infection arm of this cohort. Both of these infant groups will have blood drawn and a nasal wash obtained on study entry and at days 10 (+ 4d/- 2d) and 24 (+/- 4d) post-vaccination and then will be followed to the subsequent influenza season and rechallenged with IIV, with blood draws and nasal washes again completed pre-vaccination and at days 10 (+ 4d/- 2d) and 24 (+/- 4d) post-vaccination (Figure 3). Children who test positive for influenza will be allowed treatment with oseltamivir as recommended by the CDC (73). To accomplish this, the rapid influenza test result will be provided to the child's pediatrician, who will then coordinate treatment of the child.

Figure 3

[figure not shown]

Figure 3: Experimental schematic to determine whether the method of initial priming differentially poises subjects to respond to future influenza encounters. Subjects that receive LAIV, IIV, or that are naturally infected with influenza will have CD4 T cell and antibody responses examined at enrollment and at days 10 and 24 post vaccination. Cohort 1 contains children approximately 24-36 months of age. Cohort 2A contains infants 6-12 months of age in their first influenza season, while cohort 2B contains infants 3-12 months of age. All enrolled subjects will be followed longitudinally for a year and then will be revaccinated with IIV. CD4 T cell responses, antibody response, and transcriptional profiles will be examined prior to revaccination and at days 10 and 24 post vaccination.

2.2: Rationale for Study Design:

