The age range of the first cohort of children was chosen because children first become eligible to receive LAIV at the age of 24 months. Thus, the age range of 24 through 35 months will capture children receiving LAIV for the first time. A block randomization scheme will be used as there is a large population of children with a past history of isolated wheezing as a result of viral illnesses such as bronchiolitis that have been shown to respond

equivalently to influenza vaccine (59, 74, 75). We feel that including this population of children in the study will improve recruitment and allow for broader applicability of our study results, but as these subjects are not eligible to receive LAIV (17, 18), their inclusion also precludes a completely blinded randomization scheme. With block randomization, eligible subjects will be enrolled to receive either LAIV or IIV in groups of 5 unless a history of isolated wheezing in the past year is present, in which case they will be defaulted to receive IIV as long as no other exclusion criteria are present.

The age range of the second cohort was chosen to enroll infants in their first influenza season with no history of prior exposure to influenza virus. Thus, this cohort will allow examination of the true primary response to influenza infection or inactivated vaccination. Children between 6 and 12 months of age who have not previously had an influenza infection or vaccination will be eligible to participate in the vaccination group. All of these children will receive IIV, as LAIV is not approved for children this age. This cohort will receive a prime-boost vaccination series, with vaccine doses separated by 28 (+ 14) days as recommended by the AAP and ACIP (17, 18). To minimize blood draws, we will only interrogate the immune response following the second vaccine dose. Children between 3 and 12 months of age who present with an influenza-like illness and have no previous history of influenza vaccination will be eligible to participate in the infection group. Study personnel will obtain nasal swabs from potential subjects for a rapid influenza antigen test on illness presentation (typically this occurs at day 3-4 post illness onset). If positive, they will be eligible for further study participation. Influenza real-time RT-PCR will be used to confirm rapid antigen test results, however these results will not be available in time to influence subject enrollment.

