- Between 6 and 12 months to participate in the vaccination arm of cohort 2 (cohort 2A)
- Between 3 and 12 months to participate in the natural infection arm of cohort 2 (cohort 2B)
- Gestational age of ≥ 37 weeks at birth
- Parent/guardian can provide informed consent
- Available for the duration of the study
- History of previous IIV administration **ONLY** for participation in cohort 1
- Acute illness documented to be due to influenza virus **ONLY** for participation in the natural infection arm of cohort 2 (cohort 2B)

b. Exclusion Criteria:

- Immunosuppression as a result of an underlying illness or condition (including HIV or a primary immunodeficiency syndrome)
- Active neoplastic disease
- Use of potentially immunosuppressive medications currently or within the past year (including chemotherapeutic agents) or chronic (>2 weeks) use of oral or inhaled steroid therapy
- A diagnosis of asthma requiring chronic controller medication
- Previous administration of influenza vaccine in the current influenza season
- Receipt of immunoglobulin or another blood product within the year prior to study enrollment
- An acute illness within the previous 3 days or temperature $>38^{\circ}$ on screening **EXCEPT** for participation in the natural infection arm of cohort 2 (cohort 2B)
- A contraindication to influenza vaccination **EXCEPT** infants between 3 and 5 months presenting with natural influenza infection whose only contraindication is their current age

3.3: Discussion of Subject Population:

The main objective of this Study is to evaluate the specificity and functional potential of the CD4 T cell response and the quantity, breadth and avidity of the neutralizing antibody response following influenza infection or vaccination. In order to eliminate potential confounding factors, we plan to exclude any subject who has an acute or chronic medical condition that may result in immunosuppression. Also excluded will be potential subjects that have recently received immunosuppressive medications or blood products that could potentially interfere with vaccine immunogenicity. This exclusion will include children with a history of asthma who require chronic controller medicines, including inhaled steroids. Children with only a history isolated wheezing not on chronic controller therapy will be allowed to participate, although they will not be administered LAIV.

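### Aim 3's overall tests pool two cohorts that share neither age nor vaccination history, and the two within-cohort comparisons that bear on priming are not singled out or powered

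*Combined protocol and SAP*

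**What the plan says.** Hypothesis 3 in Section 1.1 reads: "The CD4 T cell responses established with this initial priming will differentially poise subjects to respond to revaccination with IIV the following influenza season". The Figure 3 caption in Section 2.1 describes an "Experimental schematic to determine whether the method of initial priming differentially poises subjects to respond to future influenza encounters".

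The groups come from two cohorts. Cohort 1 (LAIV 30, IIV 30) takes "children who have previously been vaccinated with at least 2 doses of IIV and who are between the ages of 24 and 35 months" (Section 2.1). Cohort 2 takes infants in their first influenza season. For its vaccination arm (30), "Children between 6 and 12 months of age who have not previously had an influenza infection or vaccination will be eligible" (Section 2.2); its infection arm (15) takes unvaccinated infants of 3 to 12 months.

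For Aim 3, Section 13.2 plans, at each year-2 time point, a one-way ANOVA over the four groups (Kruskal-Wallis if normality is rejected), after which Tukey's "adjustment will be used to test for significant differences between groups". It adds: "We will also apply a linear mixed effect model similar to Equation (1.1) to detect the overall group effect". On multiplicity: "Benjamini-Hochberg procedure will be used to control FDR at a 0.05 level for all analyses". No Aim 3 contrast, covariate or cohort term is named. Section 13.1 gives one power figure for Aim 3, 0.851, for groups of 30, 30, 30 and 15 with within-group SD 0.4 and between-group SD 0.2.

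**The concern.** The ages do not overlap at entry. About a year later they still do not: the oldest infant is then about 24 months and the youngest cohort 1 child about 36. Vaccination history before priming also differs by design. The F-test, the mixed-model overall effect and the four cross-cohort pairs therefore mix priming with age and earlier exposure. A difference caused by age alone could be reported as an effect of priming.

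A covariate cannot repair this. Cohort is the sum of two group indicators, so a cohort term is not estimable beside them, and an age term would have to extrapolate across the gap between 12 and 24 months. Only the choice of contrasts, and how they are read, can change.

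Two pairs avoid the problem: LAIV v IIV in cohort 1, and IIV v infection in cohort 2. The plan does not mark them out, charges them a six-pair penalty, and does not state their power. The mixed model has no stated pairwise follow-up at all.

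**Working it through.** **Inputs.** From Section 13.1: SD 0.4 log10; n = 30, 30, 30, 15 (error df 105 - 4 = 101); year-1 differences of 0.3 (LAIV v IIV) and 0.4 (IIV v infection). Two-sided 0.05 is inferred, because it reproduces all 18 cells of the power table. Assumed here: the year-1 differences persist to year 2; no dropout; no FDR step unless stated.

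**1. The plan's figure.** Omnibus power is the noncentral F tail with 3 and 101 df and λ = Σ nᵢ(μᵢ - μ̄)²/0.4². With three equal groups and the infection group 0.4 away (between-group SD 0.2, divisor k - 1), λ = 12.857 and power is 0.852, against the stated 0.851. In that pattern LAIV and IIV do not differ, so the figure carries no information on that pair.

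**2. Pure cohort shift, no difference inside either cohort.** The cohorts contribute 60 and 45 children, so λ = (60 × 45/105) s²/0.16 = 160.7 s².

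| Assumed shift s (log10) | λ | F-test rejects |
|---|---|---|
| 0.1 | 1.61 | 0.16 |
| 0.2 | 6.43 | 0.53 |
| 0.4 | 25.71 | 0.99 |

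Tukey flags a within-cohort pair in only about 2% of such trials.

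**3. Power of the two within-cohort pairs.** Noncentrality is d/(0.4√(1/n₁ + 1/n₂)): 2.905 for 30/30 with d = 0.3, and 3.162 for 30/15 with d = 0.4. The Tukey critical value is 3.694/√2 = 2.612. Bonferroni over two contrasts uses t at two-sided 0.025: 2.301 (58 df), 2.323 (43 df) or 2.275 (pooled 101 df).

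| Pair | Unadjusted (13.1) | Tukey | Bonferroni, two contrasts |
|---|---|---|---|
| LAIV v IIV, d = 0.3 | 0.815 | 0.616 | 0.726-0.735 |
| IIV v infection, d = 0.4 | 0.871 | 0.708 | 0.796-0.811 |

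**4. Range.**
- If both differences shrink to 0.2: Tukey 0.26 and 0.16; contrasts (101 df) 0.37 and 0.25.
- With 20% dropout (assumed; 24/24/24/12): Tukey 0.49 and 0.58; contrasts 0.61 and 0.69 (0.685).
- After Benjamini-Hochberg over six independent response variables (assumed), of which 6, 3 or 1 truly differ: LAIV v IIV 0.68, 0.58 or 0.48 as a contrast, against 0.54, 0.45 or 0.37 under Tukey.

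**5. The mixed model.** The model equation in 13.2 (printed as 0.1, cited as 1.1) has a time random effect and independent errors, but no subject effect. Simulating that error structure with four group indicators, a likelihood ratio test and an assumed within-subject correlation of 0.3 to 0.7 gives rejection of 0.19 to 0.36 with no difference anywhere. At a cohort shift of 0.1 it rejects in about 0.53 to 0.63.

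**6. Age inside cohort 2.** Infants of 3-5 months occur only in the infection arm; with ages uniform in each range (assumed), they are about 5 of the 15. If age explains no variance, adjusting for it lowers the contrast's power to 0.73 on average (42 df; 5th-95th percentile of age draws 0.62-0.79). Restriction to 6-12 months (about 30 v 10) gives about 0.65.

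**The case against.** The strongest reply is that the plan already does what is needed. Section 13.2 commits in advance to Tukey, which covers both within-cohort pairs and is hardly misled by a cohort shift. This stands. A reader might infer that these comparisons are not prespecified; the documents do not support that. They are planned, but not singled out.

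A reader might also infer that 0.851 is an error. It is not: it reproduces to within 0.001 as omnibus power. Nor are 0.62 and 0.71 the plan's own shortfall. They borrow year-1 differences, because the documents give no year-2 pairwise effect. At 0.2 both Tukey and the named contrasts would be weak.

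Exposure history is itself a stated interest (Section 2.1 objectives; Section 5.7 for RNA-seq), so cross-cohort results should not be discarded. That is right, and the fix keeps them. The cohort 1 contrast is also not one of first exposure, since those children have already had IIV.

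Section 10.1 says personal information is collected partly to account for confounders in analysis. Section 13 contains no such step, and across the cohorts none could work.

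Finally, age adjustment in cohort 2 removes most of the power gain there: 0.73 against Tukey's 0.71, and below Tukey in 27% of simulated age draws. That is a reason to make it a sensitivity analysis rather than the main test.

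**Conclusion.** The point holds as one of attribution and emphasis. The overall Aim 3 tests cannot separate priming from age and prior vaccination; this follows from the eligibility criteria and needs no effect size. How often they would mislead depends on the cohort shift, which is assumed here (0.16 to 0.99 over 0.1 to 0.4 log10).

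The power argument is conditional on the year-1 differences persisting. On that basis, naming the two contrasts raises LAIV v IIV by 11-12 points, to about 0.73, which is still under 0.80. It raises the unadjusted IIV v infection contrast by 9-10 points, to 0.80-0.81. The missing subject effect is a separate defect of the mixed model and would distort its p-values even if the cohorts were alike.

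The plan should be changed, but the change is one of wording. No design error is alleged.

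**What to change.** In Sections 13.2 and 13.1:

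1. Name LAIV v IIV within cohort 1 and IIV v infection within cohort 2 as the Aim 3 tests of priming at each year-2 time point. Use the unadjusted t-test or rank-sum test, as in Aims 1 and 2. Apply Bonferroni over the two, then Benjamini-Hochberg across response variables, separately for each contrast.
2. In the Aim 3 mixed model, use one indicator per group, add a subject random effect, and test the same two contrasts in place of the overall effect.
3. Keep the omnibus test and the four cross-cohort comparisons as secondary results on exposure history, with confidence intervals. State that they mix priming, age and prior vaccination and are not evidence of a priming effect.
4. As sensitivity analyses for cohort 2, adjust for age at priming and repeat the contrast in infants aged 6-12 months. Say that the adjustment extrapolates for the 3-5 month olds.
5. State the power of the two contrasts beside 0.851, with the assumed year-2 differences and a range.

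**Cost.** Text only. Age is an eligibility item and so is already recorded, and the four-group model must be written out anyway because the printed equation has a binary group variable. Cross-cohort tests become secondary, and the age-adjusted cohort 2 estimate is less precise. Some confounding remains: cohort 2 is not randomised, and cohort 1 children with recent wheezing default to IIV.
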